Study Visit Schedule and Procedures Continued	
Treatment: Week 1 to Week 6
 
After the WO Period, eligible subjects will be stratified based on screening plasma angiotensinogen (AGT) concentration ($\leq 30 \mu\text{g/mL}$ vs $> 30 \mu\text{g/mL}$) and randomized 2:1 to 80 mg ISIS 757456 or placebo. Subjects will receive SC doses of Study Drug on Study Days 1, 3, 8, 15, 22, 29, and 36. Subjects will remain off antihypertensive medications for approximately 3 months throughout the study.
 
Subjects that discontinue treatment may remain in the study and will attend the Study Day 43 visit.
 
Post-Treatment: Week 7 to Week 19
 
Subjects are to return to the Study Center for follow-up visits on Study Days 43, 50, 64, 78, 106 and 127. The final study visit will be Study Day 127 (Week 19).

Primary Endpoint	Percent change in plasma angiotensinogen from Baseline to Study Day 43 (Week 7) compared to placebo
Secondary Endpoints	Change on in-clinic SBP from Baseline to each scheduled, post-Baseline visit Change and percent change in plasma angiotensinogen from Baseline to each scheduled, post-baseline visit
Safety Endpoints	Incidence and severity of treatment-emergent adverse events (TEAE) (including hypotension and orthostatic hypotension), use of concomitant medications, laboratory assessments, ECG, and vital signs

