8.6.5. Stopping Rule for Blood Pressure

1. In the event of a SBP ≤ 90 mmHg with symptoms of hypotension (i.e., dizziness, light-headedness, clammy skin, fatigue, blurry vision), as measured by home BPM, at any point in the study, the patient should contact the Study Center immediately and have the SBP confirmed by the Study Center. If confirmed and the patient remains symptomatic, dosing of a subject with Study Drug will be interrupted. If patient is still symptomatic after instituting IV hydration (see Section 8.5.3 Safety Monitoring Rules for Blood Pressure), the patient should be admitted to the hospital. Timing for re-institution should be assessed depending on the reversibility of initiating factors (decreased oral intake, cold/flu, other illness). If the subject remains symptomatic Study Drug should be stopped permanently. If this occurs in the follow-up period, any other antihypertensives or other medications that could affect BP should be stopped, if feasible. The use of IV angiotensin II or vasopressors should be considered in subjects that remain symptomatic and are hemodynamically unstable. The subject will continue to be followed per protocol

in the study. Follow-up for subjects that screen fail due to blood pressure inclusion criteria (see Section 5.1) will not be necessary.

2. During the Treatment Period, should a subject experience a BP measurement > 170 mmHg (systolic) or > 110 mmHg (diastolic) a second measurement must be done within a 30-minute period. If the subject's BP is >170 mmHg (systolic) or > 110 mmHg (diastolic) within the 30-minute period, an additional BP measurement should be taken within 48 hours at the Study Center, regardless of whether the initial BP measurements were taken in clinic or at home. If the subject then experiences a BP measurement > 170 mmHg (systolic) or > 110 mmHg (diastolic) (confirmed by triplicate measurement at the Study Center), they will then be withdrawn from further blinded, randomized treatment. The subject's pre-study antihypertensive medication(s) may be added back per Investigator and Sponsor Medical Monitor judgement. The subject will continue to be followed per protocol in the study.

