8.10.1.1. Allowed Concomitant Therapy

Any other medications deemed necessary by the Investigator are allowed except those listed in the disallowed concomitant therapy.

If the criteria in Section [8.5.3](#) (blood pressure monitoring rules) are met and the patient is in the Post-Treatment Period, antihypertensive agents may be added for BP control in consultation with the Investigator and Sponsor Monitor or designee.

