10.3. Populations

Full Analysis Set (FAS): All randomized subjects who have received at least 1 injection of Study Drug (ISIS 757456 or Placebo) and who have at least 1 post-Baseline efficacy or exploratory measurements.

Per Protocol Set (PPS): All FAS subjects who received at least 5 of the 7 doses of Study Drug, did not receive antihypertensive medications during the Treatment Period and prior to Study Day 43, and have no significant protocol deviations that would be expected to affect efficacy or exploratory assessments.

Safety Set: All subjects who are randomized and receive at least 1 dose of Study Drug.

PK Set: All subjects who are randomized and receive at least 1 dose of Study Drug and have at least 1 evaluable PK sample.

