10.6.5. Exploratory Analyses

The change of the weekly average of at-home BP from Baseline to each schedule post-Baseline visit, and the change and percent change from Baseline to each schedule post-Baseline visit in angiotensin II, renin (Plasma renin activity [PRA]; active renin mass concentration [ARC]), and plasma aldosterone will be compared between ISIS 757456 80 mg group and placebo group in PPS and FAS. The data will be analyzed in a similar way to the primary analysis.

The percentage of subjects reaching the following goals for the in-clinic BP over time will be summarized, comparison of which will be made between ISIS 757456 80-mg group and placebo group using Fisher's exact test.

- Percentage of subjects reaching SBP goal of ≤ 140 mmHg
- Percentage of subjects reaching DBP goal of ≤ 90 mmHg
- Percentage of subjects reaching both goals of SBP ≤ 140 mmHg and DBP ≤ 90 mmHg

In addition, the percentage of subjects requiring antihypertensive therapy during the study, as well as the time in days from first dose of Study Drug to the first administration of antihypertensive therapy during the study will be compared between ISIS 757456 80-mg group and placebo group in PPS and FAS. The analyses will be detailed in the SAP.

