3.3 Statistical Methods

3.3.1 Subject Populations Analyzed

The following analysis populations are defined for this study:

- Full Analysis Set (FAS): All randomized subjects who have received at least 1 injection of Study Drug (ISIS 757456 or Placebo) and who have at least 1 post-Baseline efficacy or exploratory measurements.
- Per Protocol Set (PPS): All FAS subjects who received at least 5 of the 7 doses of Study Drug, did not receive antihypertensive medications during the Treatment Period and prior to Study Day 43, and have no significant protocol deviations that would be expected to affect efficacy or exploratory assessments.

- Safety Set: All subjects who are randomized and receive at least 1 dose of Study Drug.
- PK Set: All subjects who are randomized and receive at least 1 dose of ISIS 757456 and have at least 1 evaluable PK sample.

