3.5.3 Exploratory Analyses

The exploratory analyses will be conducted using the PPS and FAS.

The change of the weekly average of at-home BP from Baseline to each schedule post-Baseline visit, and the change and percent change from Baseline to each schedule post-Baseline visit in angiotensin II, renin (Plasma renin activity [PRA]; active renin mass concentration [ARC]), and plasma aldosterone will be compared between ISIS 757456 80 mg group and placebo group. The data will be analyzed in a similar way to the primary analysis. For the at-home BP analysis, subsequent SBP and DBP measurements will be completely removed from this exploratory analysis once the subjects received first administration of antihypertensive therapy during the study.

The percentage of subjects reaching the following goals for the in-clinic BP over time will be summarized, comparison of which will be made between ISIS 757456 80-mg group and placebo group using Fisher's exact test. Subsequent SBP and DBP measurements will be completely removed from this exploratory analysis once the subjects received first administration of antihypertensive therapy during the study.

- Percentage of subjects reaching SBP goal of ≤ 140 mmHg
- Percentage of subjects reaching DBP goal of ≤ 90 mmHg
- Percentage of subjects reaching both goals of SBP ≤ 140 mmHg and DBP ≤ 90 mmHg

The antihypertensive therapy will be identified through medical review when database is locked. The percentage of subjects requiring antihypertensive therapy during the study will be compared between ISIS 757456 80 mg group and placebo group in PPS and FAS using Chi-Square test or Fisher's exact test as appropriate. The time in days from first dose of Study Drug to the first administration of antihypertensive therapy during the study will be summarized using the following descriptive statistics: mean, standard deviation, median, P25, P75, and minimum and maximum. The Kaplan-Meier curves [1] for time to the first administration of antihypertensive therapy will be provided for ISIS 757456 80 mg group and placebo group, comparison of which may be made statistically using the log rank test. The time to the first administration of antihypertensive therapy will be calculated as:

- [Date of the first administration of antihypertensive therapy – Date of first dose of study drug +1]

Patients who did not receive any antihypertensive therapy during the study will be censored at the date of end of study.

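### The PPS version of the antihypertensive-therapy endpoint selects on its own outcome: on the natural reading of the PPS definition it can contain no event before Day 43

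*Combined protocol and SAP*

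**What the plan says.** **Endpoint and sets.** SAP 3.5.3 opens by stating "The exploratory analyses will be conducted using the PPS and FAS". It then specifies that the share of patients "requiring antihypertensive therapy during the study will be compared between ISIS 757456 80 mg group and placebo group in PPS and FAS", by chi-square or Fisher's exact test. It adds descriptive statistics and Kaplan-Meier curves for the time from first dose to first antihypertensive use, with an optional log-rank test. Protocol 10.6.5 likewise says that the interval between first dose and "first administration of antihypertensive therapy during the study will be compared between ISIS 757456 80-mg group and placebo group in PPS and FAS".

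**Membership of the PPS.** SAP 3.3.1 and protocol 10.3 use the same definition. It begins "All FAS subjects who received at least 5 of the 7 doses of Study Drug", then requires that the subject "did not receive antihypertensive medications during the Treatment Period and prior to Study Day 43" and has no significant protocol deviation expected to affect efficacy or exploratory assessments.

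**Early therapy is foreseen.** Protocol 8.6.5, item 2, applies during the Treatment Period. After a blood pressure above 170 systolic or 110 diastolic is confirmed at the Study Center, the subject is withdrawn from randomized treatment and the subject's "pre-study antihypertensive medication(s) may be added back per Investigator and Sponsor Medical Monitor judgement". Protocol 6.1.4 says that any reinstated antihypertensives will be recorded on the concomitant medications eCRF.

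Neither document sets a Day 43 landmark for this endpoint or mentions the overlap.

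**The concern.** The event being counted is also a reason for exclusion from one of the two sets in which it is counted. Membership is settled after randomization, by the outcome itself, and treatment may influence that outcome. A PPS analysis beside a FAS analysis is usually read as a check on robustness. Here, agreement or disagreement between the two would say little about robustness, because the PPS has had the early part of the outcome removed. With about 30 subjects randomized 2:1, a few such exclusions visibly move a percentage.

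**Working it through.** The plan states no event rate or power for this endpoint, so there is no figure to reproduce. The first two steps follow from the definitions; the other two use assumed counts to show size.

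**1. Earliest possible PPS event time.** SAP 3.5.3 defines time as event date - first-dose date + 1, so an event on Study Day d has time d. The Treatment Period is Weeks 1 to 6 (Protocol Synopsis), so the PPS clause covers Days 1 to 42. The earliest PPS event is on Day 43: 43 - 1 + 1 = 43 days. The PPS curve is thus fixed at 100% for 42 of the 127 scheduled days (42/127 = 33%).

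**2. The dose rule acts in the same direction.** The Synopsis states: "Subjects will receive SC doses of Study Drug on Study Days 1, 3, 8, 15, 22, 29, and 36". The fifth dose is on Day 22. A subject withdrawn under 8.6.5, item 2, before then also fails the 5-of-7 rule, however the antihypertensive clause is read.

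**3. Effect on the percentage.** Assumptions: 10 placebo and 20 active subjects (30 at 2:1); 3 placebo and 5 active events from Day 43 on; exclusion for early therapy only. With early events e_P and e_A:

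- FAS difference = (3 + e_P)/10 - (5 + e_A)/20
- PPS difference = 3/(10 - e_P) - 5/(20 - e_A)

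| Early events (placebo, active) | FAS | Difference | PPS | Difference | PPS minus FAS |
|---|---|---|---|---|---|
| (0,0) | 3/10 vs 5/20 | 5.0 | 3/10 vs 5/20 | 5.0 | 0 |
| (1,2) | 4/10 vs 7/20 | 5.0 | 3/9 vs 5/18 | 5.6 | +0.6 |
| (1,0) | 4/10 vs 5/20 | 15.0 | 3/9 vs 5/20 | 8.3 | -6.7 |
| (3,1) | 6/10 vs 6/20 | 30.0 | 3/7 vs 5/19 | 16.5 | -13.5 |
| (0,1) | 3/10 vs 6/20 | 0.0 | 3/10 vs 5/19 | 3.7 | +3.7 |
| (0,3) | 3/10 vs 8/20 | -10.0 | 3/10 vs 5/17 | 0.6 | +10.6 |

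Differences are placebo minus active, in percentage points. In case (3,1) the two-sided Fisher p is 0.139 in the FAS and 0.635 in the PPS.

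**4. Effect on time to therapy, case (3,1).** Assumed event days: placebo 20, 30, 38, 66, 80, 108; active 25, 68, 78, 90, 106, 115; all others censored at Day 127.

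- Mean time among treated subjects, FAS: placebo 342/6 = 57.0, active 482/6 = 80.3, gap 23.3 days.
- Same, PPS: placebo 254/3 = 84.7, active 457/5 = 91.4, gap 6.7 days.
- Log-rank, FAS: observed minus expected (placebo) 2.793, variance 2.333, chi-square 3.343, p = 0.068.
- Log-rank, PPS: 1.054, variance 1.470, chi-square 0.756, p = 0.385.
- FAS split at Day 42: early part 1.739 (variance 0.863); later part 1.054 (variance 1.470), identical to the PPS.

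On this exclusion alone, the PPS log-rank is the FAS log-rank with its early part deleted, because early-treated subjects have already left the FAS risk set by Day 43.

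**The case against.** **Early events may be few or none.** Add-back in the Treatment Period needs a confirmed reading above 170 or 110 mmHg, and subjects enter with Day -7 systolic pressure of at most 165 mmHg (protocol 5.1, criterion 11). The lower 140/90 threshold in 8.5.3, item 3, applies only from Day 64. Most protocol-driven events may therefore fall where the PPS still counts them, and case (3,1) needs 3 of 10 placebo subjects to restart therapy within 42 days. This stands, and it limits the practical weight. It does not make the PPS version interpretable if early events do occur.

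**The clause can be read more narrowly.** Taken as strictly conjunctive, it excludes only use that falls both in the Treatment Period and before Day 43. Protocol 6.1.4 and 6.1.5 move early stoppers into post-treatment follow-up after their last dose. A subject who stops after the fifth dose and restarts therapy before Day 43 could then stay in the PPS. This is possible but less natural, and it would rescue only a few subjects.

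**Stronger readings that the documents do not support.** A reader might infer that:

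- the PPS analysis is empty; it still records events from Day 43 to Day 127.
- PPS and FAS can differ only through early therapy; the PPS also drops subjects for fewer than 5 doses or significant deviations.
- the bias always shrinks a benefit; with more early use on active it goes the other way.
- the protocol flatly contradicts itself on add-back. Protocol 8.10.1.1 says that if the blood pressure monitoring criteria "are met and the patient is in the Post-Treatment Period, antihypertensive agents may be added for BP control", and 8.10.1.2 limits the exception in the same way, while 8.6.5 provides for add-back in the Treatment Period. Because that add-back follows withdrawal from treatment, 6.1.4 and 6.1.5 allow such a subject to be regarded as already post-treatment. What remains is wording to reconcile.

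**Conclusion.** The point holds as a design flaw in one exploratory analysis. On the natural reading of the PPS definition, the absence of PPS events in Days 1 to 42 is certain and needs no assumption about the data. The size and direction of the resulting shift cannot be known from the documents. The tabulated values rest on assumed counts and on this exclusion alone, and a different choice of cases would give a different spread. Without early events the antihypertensive clause has no effect. The FAS analysis of the same endpoint is sound on this point, the log-rank test is optional, and the primary angiotensinogen comparison does not use this endpoint. A correction is worth making because it is cheap and removes a result that could be mistaken for confirmation or contradiction of the FAS.

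**What to change.** 1. In SAP 3.5.3, analyse the percentage and the time to first antihypertensive use in the FAS (or the Safety Set) only. Alternatively, keep the PPS version under the label *therapy from Day 43 onward among subjects untreated before Day 43*, and state that it is not a sensitivity analysis of the FAS result.
2. Record the same change against protocol 10.6.5, by amendment or as a stated departure in the SAP.
3. Minor: state that event-free subjects are censored at their own last study visit. SAP 3.5.3 censors them at the end of study, which is naturally read as the subject's own, but protocol 3.5 uses that term for the last visit of the last subject.
4. Minor: reconcile protocol 8.6.5, 6.1.4, 6.1.5, 8.10.1.1 and 8.10.1.2 on whether add-back after withdrawal from treatment counts as Treatment Period or Post-Treatment Period use, since PPS membership can turn on it.

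The cost is a few sentences and no new data. If the SAP is already final, its section 1 provides for documenting the deviation in the clinical study report.

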1.2.4. Exploratory Endpoint

- Change of the weekly average of at-home BP from Baseline to each scheduled, post-baseline visit
- Change and percent change of angiotensin II, renin (Plasma renin activity [PRA]; active renin mass concentration [ARC]), and plasma aldosterone from Baseline to each scheduled, post-baseline visit
- Percentage of subjects reaching the goals of in-clinic SBP \leq 140 mmHg, DBP \leq 90 mmHg, and both over time
- Percentage of subjects and time to requiring antihypertensive therapy during the study
- Assessments of urinary analytes (e.g., cortisol, aldosterone, angiotensin II, albumin, creatinine, protein and sodium) from Baseline to each scheduled, post-baseline visit may be performed
- PK parameters including but not limited to C_{max} (maximum observed ISIS 757456 plasma concentration), T_{max} (time to maximal plasma concentration) and AUC (area under the plasma concentration time profile for ISIS 757456)
- Potential exposure-response analysis using relevant exposure parameters and biomarkers including, but not limited to C_{trough} and plasma AGT may be performed

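### The plain mean, SD, median and quartiles planned for time to first antihypertensive therapy do not estimate a censored time and tend to understate a between-arm difference

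*Combined protocol and SAP*

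**What the plan says.** The protocol (1.2.4) lists this exploratory endpoint: "Percentage of subjects and time to requiring antihypertensive therapy during the study". Protocol 10.6.5 commits to comparing both parts between the arms and leaves the detail to the SAP.

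SAP 3.5.3 then sets out the following:

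- **Percentage restarting.** "The percentage of subjects requiring antihypertensive therapy during the study will be compared between ISIS 757456 80 mg group and placebo group", by a chi-square or Fisher's exact test, in the PPS and the FAS.
- **Descriptive summary of the time.** The time in days "will be summarized using the following descriptive statistics: mean, standard deviation, median, P25, P75, and minimum and maximum".
- **Curves.** "The Kaplan-Meier curves [1] for time to the first administration of antihypertensive therapy will be provided" for each arm, "comparison of which may be made statistically using the log rank test".
- **Definition of the time.** "Date of the first administration of antihypertensive therapy – Date of first dose of study drug +1".
- **Censoring.** "Patients who did not receive any antihypertensive therapy during the study will be censored at the date of end of study".

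The SAP does not say which subjects enter the descriptive summary, or whether its median and quartiles are Kaplan-Meier estimates.

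**The concern.** The time is defined only when there is a restart date. A subject who never restarts has none and is censored, and SAP 3.3.2 rules out imputation. A plain mean or quartile therefore has two possible readings, and neither gives the time to therapy in the arm.

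- **Restarters only (the natural reading).** The statistic conditions on having had the event. An arm in which few subjects restart is described by those few, and the subjects who stayed off therapy, who carry most of the information about delay, drop out of the table.
- **Censored times counted as if observed.** The subjects who never restarted are treated as having restarted on their last day, so the time is understated and the upper quantiles pile up at the end of follow-up.

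At stake is the only numerical summary of the time that the SAP firmly commits to. The Kaplan-Meier commitment is to curves, with no stated median, event-free proportion or confidence interval, and the log-rank test is optional.

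**Working it through.** The documents state no restart rate, hazard ratio or power for this endpoint, so there is no figure to reproduce. What follows is an illustration.

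**Inputs from the documents.** About 30 subjects (protocol 3.3) randomized 2:1 (protocol 3.1), so about 20 active and 10 placebo. The final visit is Day 127 (protocol 3.4.4). With the +1 in the formula, the time in days equals the study day.

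**Assumptions.** A constant restart hazard from day *s* to Day 127, with cumulative restart probability *p* by Day 127: 50% to 90% on placebo and 20% to 60% on active. Two starting days are used:

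- *s* = 64, because protocol 8.5.3 lowers the blood pressure threshold for adding medication back from 170/110 to 140/90 mmHg on Day 64, and entry requires a systolic pressure above 140 mmHg off medication on Day -7.
- *s* = 1, because protocol 8.6.5 and 8.5.3 also allow medication to be added back earlier, and protocol 3.1 describes add-back after treatment without a Day 64 limit. This case concerns the FAS, since the PPS excludes subjects given antihypertensives during treatment and before Day 43.

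**Formulas**, with L = 127 − s and h = −ln(1 − p)/L:

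- mean among restarters = s + 1/h − L(1 − p)/p
- restricted mean to Day 127 = s + p/h
- Kaplan-Meier median = s + ln 2/h, if this is at most 127

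**Worked case**, s = 64, L = 63:

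- p = 0.8: 1/h = 63/1.609 = 39.14. Restarters' mean = 64 + 39.14 − 15.75 = 87.4. Restricted mean = 64 + 0.8 × 39.14 = 95.3.
- p = 0.2: 1/h = 63/0.2231 = 282.3. Restarters' mean = 64 + 282.3 − 252 = 94.3. Restricted mean = 64 + 0.2 × 282.3 = 120.5.
- Difference: 6.9 days among restarters, 25.2 days by restricted mean.

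**All cases** (days, placebo then active; differences taken before rounding):

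| s | p placebo / active | Restarters' mean | Difference | Restricted mean | Difference |
|---|---|---|---|---|---|
| 1 | 90% / 60% | 41.7, 54.5 | 12.8 | 50.2, 83.5 | 33.3 |
| 1 | 80% / 40% | 47.8, 58.7 | 10.9 | 63.6, 99.7 | 36.0 |
| 1 | 80% / 20% | 47.8, 61.7 | 13.9 | 63.6, 113.9 | 50.3 |
| 1 | 60% / 30% | 54.5, 60.3 | 5.8 | 83.5, 107.0 | 23.5 |
| 1 | 50% / 20% | 56.8, 61.7 | 4.9 | 91.9, 113.9 | 22.0 |
| 64 | 90% / 60% | 84.4, 90.8 | 6.4 | 88.6, 105.3 | 16.6 |
| 64 | 80% / 40% | 87.4, 92.8 | 5.4 | 95.3, 113.3 | 18.0 |
| 64 | 80% / 20% | 87.4, 94.3 | 6.9 | 95.3, 120.5 | 25.2 |
| 64 | 60% / 30% | 90.8, 93.6 | 2.9 | 105.3, 117.0 | 11.7 |
| 64 | 50% / 20% | 91.9, 94.3 | 2.4 | 109.4, 120.5 | 11.0 |

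The restarters' difference is 2.4 to 13.9 days, against 11.0 to 50.3 days by restricted mean. As a share this runs from 22% (4.9/22.0) to 38% (12.8/33.3).

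**Sampling error.** In 20,000 simulated trials for each of three rate pairs (80%/40%, 80%/20%, 60%/30%) and both starting days, the active restarters' mean was no later than the placebo restarters' mean in 27% to 40% of trials, despite a true delay. At 20% restarting, the active mean and SD rest on about 0.2 × 20 = 4 subjects.

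**The two readings compared.** In the 20% arm with s = 64, a restarters-only table shows Day 94.3. Counting censored times as observed, with full follow-up to Day 127, shows Day 120.5. One SAP sentence thus allows tables 26.2 days apart.

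**The case against.** The strongest reply is that the descriptive summary does not stand alone. Just before it, the SAP firmly plans a test of the percentage restarting. Just after it come Kaplan-Meier curves by arm and a censoring rule. With 80% against 20% restarting, the contrast would be plain in the percentages and in the curves. This stands. A reader might infer that the plan hides the difference, or that its users would conclude the drug does not delay restarting. Neither follows for the plan as a whole.

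Two further replies also stand in part. First, the SAP never says that the table is limited to restarters; that is inferred from the formula. But the other reading is no sounder as a time to therapy, so the ambiguity is itself a reason to edit the sentence. Second, restart rates and the starting day are assumed. With a Day 1 start the restarters' means differ by up to 13.9 days in the right direction, so they are attenuated rather than equal.

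It is also fair that this is one table for an exploratory endpoint, and that no primary or secondary result depends on it.

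**Conclusion.** The point holds for the descriptive table only. As written, the plain mean, SD, median and quartiles do not estimate time to therapy in either arm. Under a constant hazard and the assumed rates, a restarters-only table shows roughly a fifth to two fifths of the restricted-mean difference, and in a trial of this size it can reverse the sign by chance. The size depends on those assumptions; with differently shaped hazards the attenuation would differ. That the statistics are conditional on restarting does not depend on the rates, only on the restarters-only reading.

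A reader might also infer that most subjects will be censored. The documents do not support this: every subject without therapy is censored, but nothing says how many that will be. Importance is low.

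**What to change.** In SAP 3.5.3, replace the raw statistics with:

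- the Kaplan-Meier median and quartiles by arm, shown as not reached where that applies, with 95% CIs;
- the Kaplan-Meier event-free proportion by arm with 95% CIs at stated days, for example Day 64 and a day near the end of follow-up;
- optionally, the restricted mean by arm, truncated at a day that follow-up in both arms reaches. The final visit window is Day 127 ± 5, so Day 127 itself may lie beyond the last observed time; Day 122 (127 − 5) is one candidate.

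Show restarters' raw times only in a listing, or in a row labelled as restarters only with n. State that the censoring date is the subject's own last visit, because protocol 3.5 defines end of study as the last visit of the last subject.

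The cost is a sentence or two of SAP text and standard output from the Kaplan-Meier procedure already planned. No data collection or trial conduct changes. The downside is that medians may not be reached (in the illustration, the active median is not reached at 40% restarting or less) and intervals will be wide with about 30 subjects.
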